3.5 If applicable, please select the Designated Department Approval(s)	
[name], [name] Department Chair Add the name of the individual authorized to approve and sign off on this protocol from your Department (e.g. the Department Chair or Dean).	
4.0	

Initial Screening Questions

Updated June 2017

4.1 * PROJECT SUMMARY: (REQUIRED) Give a brief overview of this project (250 words or less). Tell us what this study is about, who is being studied, and what it aims to achieve. If you have an NIH Abstract, paste it here: Click on the orange question mark to the right for more detailed instructions.

BACKGROUND:

There is a need for cost-effective infertility treatments. For women requiring in-vitro fertilization (IVF), intra-vaginal culture (IVC) of embryos can be used as a lower-cost alternative, using the INVOcell® device.

HYPOTHESIS:

In women with infertility requiring IVF, we will see similar clinical pregnancy rates (CPR) with minimal gonadotropin or oral medication stimulation using the INVOcell device compared with conventional IVF.

PRIMARY AIM:

To determine outcomes of IVC with INVOcell device versus conventional IVF while using oral stimulation or minimal gonadotropins stimulation protocols:

a. Implantation rate	
SECONDARY AIMS: To determine the effect of IVC with INVOcell device versus conventional IVF while using oral stimulation or minimal gonadotropins stimulation protocols on:	
a. Fertilization rateb. Embryo qualityc. Clinical pregnancy rated. Live birth rate	
DESIGN Non-blinded prospective randomized controlled trial pilot study	
4.2 * HUD DEVICE: (REQUIRED) Does this application involve a Humanitarian Use Device (HUD):
NoYes, and it includes a research componentYes, and it involves clinical care ONLY	
4.3 * TYPE OF RESEARCH: (Click the Help link for definitions and guidance): (REQUIRED)	
 Biomedical research Social, behavioral, educational, and/or public policy research Hybrid - includes aspects of BOTH types of research (check this option if your research is mainly social/behavioral but also involves specimen collection or blood draws to look at biological measures) 	
4.4 * SUBJECT CONTACT: (REQUIRED) Does this study involve ANY contact or interactions participants:	with
Yes (including phone, email or web contact)No (limited to medical records review, biological specimen analysis, and/or data analysis)	

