IVC, also called INVO, was developed by Claude Ranoux in 1988 as another method for culturing oocytes or embryos when compared to the conventional laboratory culture method [5]. Since then, the device has been used and studied in multiple countries including: Austria, Bolivia, Brazil, Canada, Ecuador, India, Mexico, Nicaragua, Pakistan, Panama, Spain, Turkey, and Venezuela [5-8]. In addition, INVOcell was FDA approved for use in the United States in November of 2015. There have been numerous studies on the INVO procedure and INVOcell device including evaluation and optimal conditions of the culture such as pH, pCO2 and pO2 [8] to optimal time of intra-vaginal culture [9]. Garcia-Ferreyra et al performed a prospective, non-randomized study that evaluated INVO using intracytoplasmic sperm injection (ICSI) with INVOcell versus conventional ICSI to day 3 and found no significant differences between embryo quality (77% INVO-ICSI versus 86.8% ICSI), pregnancy rate (54.2% INVO-ICSI versus 58.1% ICSI) and implantation rate (31.7% INVO-ICSI versus 33.6% ICSI) [10]. To control for factors between patients, a pilot study performed in 2015, compared sister ocytes (INVO vs IVF) and found similar cleavage rates (93% ± 1.5% IVF versus 97% ± 6% INVO) and a clinical pregnancy rate of 43% per embryo transferred from INVO procedure. In the United States, the device has been FDA approved for IVC for three days, but there is currently research being done to investigate whether IVC for five days (to blastocyst stage) can lead to improved embryo quality and live birth rates. Doody et al performed a randomized controlled trial comparing IVF to IVC that showed no significant differences in the percentage quality of blastocyst transferred when compared to IVF (87.9% IVC, 97.2%, p = 0.09) and live birth rate (55 % IVC, 60 % IVF) [9]. In fact, the implantation and birth rates per blastocyst transferred was actually higher with INVOcell wersus IVF (54.5 versus 44.4% and 48.5 versus 41.7%) [9]. These findings are promising and show that	
7.7 * TREATMENT PROTOCOL: Is this a treatment study, i.e. does this study intend to provid to individuals with a medical or psychological condition: (REQUIRED)	e treatment
⊙ Yes ○ No	
7.8 * COMMON RESEARCH ACTIVITIES: Types of research activities that will be carried out. apply and describe in more detail in the 'Procedures / Methods' section: (REQUIRED)	Check all that

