We expect N=20 to each group (cases and controls, respectively) and given low-stimulation protocols, expect 1-3 embryos per patient. Given these low numbers, summary statistics will be used. For categorical outcomes, frequency tables will be provided. For continuous outcomes, full summary statistics will be provided. This will include mean, standard deviation, minimum, maximum, median and quartiles. To determine the effect of IVC with INVOcell device versus conventional IVF while using oral stimulation or minimal gonadotropins stimulation protocols on: a. Fertilization rate, which is defined by the total number of fertilized oocytes divided by total number of mature oocytes retrieved. This comparison will take place on day-3, as that is when the IVC embryos will be assessed. b. Embryo quality. This is measured by the Gardner grading system. c. Implantation rate, which is defined by number gestational sacs seen on early pregnancy 6-week ultrasound divided by number of embryos transferred. d. Clinical pregnancy rate, which is defined by the number of fetal poles with heartbeat seen on ultrasound divided by the number of embryos transferred. e. Live birth rate, which is defined by the number of living babies delivered divided by the number of transfers. To determine the effect of IVC with INVOcell device versus conventional IVF while using oral stimulation or minimal gonadotropins stimulation protocols on: a. Live birth rate, which is defined by the number of live births divided by the number of transfers		ill be

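### Section 7.25 aims to determine the effect of IVC versus IVF but plans only per-arm tables and summaries; add each between-arm difference with an interval that allows for several embryos or oocytes per woman.

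*Combined protocol and SAP*

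**What the plan says.** Section 7.25 (Statistical Methods) calls the study a pilot that may lead to a larger randomized trial. It says "Given these low numbers, summary statistics will be used. For categorical outcomes, frequency tables will be provided", and for continuous outcomes it lists the mean, standard deviation, minimum, maximum, median and quartiles. The same section states a comparative aim, "To determine the effect of IVC with INVOcell device versus conventional IVF", and applies it to fertilization, embryo quality, implantation, clinical pregnancy and live birth. The hypothesis in section 4.1 is also comparative: "we will see similar clinical pregnancy rates (CPR".

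The definitions in 7.25 fix the unit of each rate:

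- Implantation is gestational sacs per embryo transferred.
- Clinical pregnancy is "the number of fetal poles with heartbeat seen on ultrasound divided by the number of embryos transferred".
- Fertilization is per mature oocyte retrieved.
- Live birth is worded twice, as "the number of living babies delivered divided by the number of transfers" and as "the number of live births divided by the number of transfers".

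Section 7.25 also says the study will "expect 1-3 embryos per patient". Sections 7.25 and 10.6 give 20 women per group, whereas 9.1 and 9.3 give 16.

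**The concern.** Every analysis named in 7.25 describes one arm at a time. The single mention of a comparison only gives the day on which fertilization is assessed. I found no IVC-minus-IVF difference, ratio, interval or margin anywhere in the document.

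A reader can subtract one tabulated rate from another, but cannot build a valid interval from arm totals. Embryos and oocytes are grouped within women, and that grouping is lost once they are totalled by arm. If the interval is wanted, the plan has to provide for it.

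Two things are at stake. Close observed rates, read beside a hypothesis of similarity, would carry no indication of how large a true difference remains possible. And the possible larger trial would receive two rates instead of an estimated difference with its uncertainty.

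**Working it through.** **The plan's own figure.** There is none to reproduce. Section 9.3 justifies the size as a pilot limit, with no error rate, power, effect size or margin. The calculation below only shows how wide the missing interval would be.

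**Inputs from the documents.** Section 7.6 reports "implantation rate (31.7% INVO-ICSI versus 33.6% ICSI" from a non-randomized day-3 ICSI study, so p1 = 0.317 and p2 = 0.336. The number of women per arm is 16 or 20.

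**Assumed inputs.** These are the number of embryos transferred per woman, m = 1 to 3 (7.25 gives embryos per patient, not embryos transferred); the within-woman correlation, ICC = 0 to 0.4; and the number of women per arm with a transfer, n. Setting n to 16 or 20 assumes a transfer in every woman. Setting n to 13 assumes that about 80% of 16 have one.

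**Formula.** Half-width = t(0.975, 2n − 2) × √{ (p1q1 + p2q2) / (n·m) × [1 + (m − 1)·ICC] }, with q = 1 − p.

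p1q1 + p2q2 = 0.317 × 0.683 + 0.336 × 0.664 = 0.2165 + 0.2231 = 0.4396.

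Example with n = 16 and m = 1: 2.042 × √(0.4396/16) = 2.042 × 0.1658 = 0.339, or 33.9 points.

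Example with n = 16, m = 3 and ICC 0: 2.042 × √(0.4396/48) = 2.042 × 0.0957 = 0.195, or 19.5 points.

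Half-widths in percentage points:

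| n per arm with a transfer | t | m = 1 | m = 2, ICC 0 / 0.2 / 0.4 | m = 3, ICC 0 / 0.2 / 0.4 |
|---|---|---|---|---|
| 13 | 2.064 | 38.0 | 26.8 / 29.4 / 31.8 | 21.9 / 25.9 / 29.4 |
| 16 | 2.042 | 33.9 | 23.9 / 26.2 / 28.3 | 19.5 / 23.1 / 26.2 |
| 20 | 2.024 | 30.0 | 21.2 / 23.2 / 25.1 | 17.3 / 20.5 / 23.2 |

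The ends of each row are extreme cases in which every woman has one embryo or every woman has three. In a simulation with 1, 2 or 3 embryos equally likely, the mean half-widths at ICC 0 / 0.2 / 0.4 were 23.8 / 26.6 / 29.1 at 16 per arm and 21.1 / 23.6 / 25.9 at 20 per arm, with a transfer in every woman. With 80% having a transfer they were 27.0 / 30.2 / 33.1 and 23.9 / 26.8 / 29.3.

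**Sensitivity to the rate.** At an assumed 15% in both arms, p1q1 + p2q2 = 2 × 0.15 × 0.85 = 0.255. With n = 16 and m = 2, the half-width is 2.042 × √(0.255/32) = 18.2 points at ICC 0. At ICC 0.4 it is 18.2 × √1.4 = 21.6 points. Simulation with mixed 1 to 3 embryos agrees, at about 18 to 22.

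**Does the proposed interval work at this size?** The woman-clustered interval for the difference in ratios, with degrees of freedom equal to contributing women minus 2, was simulated with 100,000 runs per setting at the 7.6 rates. Coverage was 0.943 to 0.948 across 16 and 20 per arm, 100% or 80% with a transfer, and ICC 0 to 0.4. One weak spot is that an arm with no events contributes zero variance. At an assumed 15% rate with 16 per arm, this happens in about 1 to 4% of runs, so a fallback is needed.

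**Live birth, if it is yes/no once per woman.** Section 7.6 gives 55% IVC and 60% IVF. With 20 transfers per arm (assumed) that is 11/20 v 12/20. The Wilson limits are 0.342 to 0.742 and 0.387 to 0.781. The Newcombe interval is:

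- lower: −0.05 − √[(0.55 − 0.342)² + (0.781 − 0.60)²] = −0.326
- upper: −0.05 + √[(0.742 − 0.55)² + (0.60 − 0.387)²] = +0.237

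The difference is −5.0 points, with a 95% interval of −32.6 to +23.7.

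**The case against.** The strongest reply is that descriptive reporting is a deliberate choice with a stated reason. The form field asks for a brief summary, the study is labelled a pilot, and no power is claimed. No decision rule hangs on the missing interval, and tables with small counts already warn the reader. Most of this stands. It supports leaving out tests, and it makes this an improvement, not an invalid analysis. It does not supply the difference, and it does not let a reader recover an interval that respects the grouping within women.

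The borrowed rates are also a loose match. The implantation rates come from a non-randomized ICSI study, and the live birth rates come from a trial that transferred blastocysts. Here transfer is on day 3, and section 12.2 allows that minimal stimulation may lower the pregnancy rate. This stands, and the widths are illustrations only. Nothing is calculated for clinical pregnancy, the outcome named in the hypothesis. As 7.25 defines it, it shares implantation's denominator, so the same formula applies, but its width depends on a rate that would have to be assumed.

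A reader might infer that the two live-birth wordings contradict each other. They need not: the second may simply restate the first. What is open is whether a twin birth counts once or twice. Section 7.14 also mentions embryos frozen for later use, without saying whether later transfers count.

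**Conclusion.** The point holds as a gap between a comparative aim and an analysis with no comparison. Under the stated assumptions, the implantation difference would carry a 95% half-width of about 20 to 34 points at 16 per arm and 17 to 30 at 20 per arm. These are ranges under assumptions, not bounds: about 18 to 22 points at an assumed 15% rate with 16 per arm and mixed 1 to 3 embryos, and wider if some women have no transfer (21.9 to 38.0 with 13 per arm).

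Two stronger readings are not supported. A reader might infer that the trial intends to declare IVC and IVF similar from these tables; 4.1 states similarity as a hypothesis, but no section announces such a conclusion or a rule for it. A reader might also infer that the pilot needs a formal test or a larger sample; nothing in the document claims power, and descriptive reporting is reasonable at this size. What should change is the reporting of the difference and its uncertainty.

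**What to change.** Keep the pilot descriptive and untested. Add to 7.25:

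> For each rate outcome the IVC-minus-IVF difference will be reported with a 95% CI. Where a woman can contribute more than one unit (embryos, oocytes, babies or transfers), the interval will be clustered on the woman, using a ratio estimator and a t reference with df equal to contributing women minus 2. Where each woman contributes one yes/no result, a Newcombe interval will be used. If an arm has no events or all events, a woman-level Newcombe interval (any event per woman, yes/no) will be reported instead. Similarity will not be concluded from this pilot.

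The sponsor should also confirm whether the two live-birth wordings in 7.25 mean the same count, and whether later frozen transfers count. The answers decide which interval applies to live birth.

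The cost is a few lines of text and minor programming from per-woman numerators and denominators. No new data or patients are needed. The downside is that the intervals will look wide.

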 □ Interviews, questionnaires, surveys □ Educational or cognitive tests □ Focus groups ☑ Observation ☑ Non-invasive imaging or testing (MRI, EEG, pulse oximetry, etc.) □ Administration of contrast agent □ Imaging procedures or treatment procedures that involve radiation (x-rays, CT scans, CT-guided biopsies, DEXA scans, MUGA or PET scan) □ Biopsy conducted solely for research purposes □ Use of placebo □ Sham surgical procedure □ Collection of data from wearable tech such as Fitbit, Apple Watch, Garmin, motion actigraphs, etc.) 	

☐ Fitness tests or other exertion activities ☐ Use of mobile health apps or other apps

☐ Social media-based research activities☐ None of the above	
7.9 * PROCEDURES / METHODS: (REQUIRED)	
For clinical research, list all study procedures, tests and treatments required for this study, including when and how often they will be performed. If there are no clinical procedures, describe the research activities.	
If some of the activities would occur even if the person were not in the study, as in the case of treatment or tests performed for diagnostic purposes, clearly differentiate between those activities that will be done solely for research purposes and those that are happening as part of routine care.	
Examples may include:	
 additional scans outside standard clinical diagnosis or monitoring additional biopsies to collect tissue for research extra clinic visits extra lab tests not required for clinical care 	
If you have a procedure table, attach it to the submission with your other study documents.	
Patients will be randomized to intra-vaginal culture (IVC) of embryos using INVOcell or traditional in-vitro fertilization (IVF) of embryos. Both groups of patients will receive the same initial workup, consultation and evaluation, ovarian stimulation, cycle monitoring, oocyte retrieval, and embryo transfer. The only difference between the two groups will be the culturing/growth of the embryos, which will be randomized to IVC or IVF. All embryos will be transferred on day 3. The IVC protocol is attached for reference.	
7.10 STANDARD CLINICAL PRACTICE: To what extent, if any, do the planned research proc from the care that people would otherwise receive at this institution or the study site done locally:	

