summary statistics will be provided. This will include mean, standard deviation, minimum, maximum, median and quartiles. To determine the effect of IVC with INVOcell device versus conventional IVF while using oral stimulation or minimal gonadotropins stimulation protocols on: a. Fertilization rate, which is defined by the total number of fertilized oocytes divided by total number of mature oocytes retrieved. This comparison will take place on day-3, as that is when the IVC embryos will be assessed. b. Embryo quality. This is measured by the Gardner grading system. c. Implantation rate, which is defined by number gestational sacs seen on early pregnancy 6-week ultrasound divided by number of embryos transferred d. Clinical pregnancy rate, which is defined by the number of fetal poles with heartbeat seen on ultrasound divided by the number of embryos transferred e. Live birth rate, which is defined by the number of living babies delivered divided by the number of transfers To determine the effect of IVC with INVOcell device versus conventional IVF while using oral stimulation or minimal gonadotropins stimulation protocols on: a. Live birth rate, which is defined by the number of live births divided by the number of transfers	We expect N=20 to each group (cases and controls, respectively) and given low-stimulation protocols, expect 1-3 embryos per patient. Given these low numbers, summary statistics will be	
a. Fertilization rate, which is defined by the total number of fertilized oocytes divided by total number of mature oocytes retrieved. This comparison will take place on day-3, as that is when the IVC embryos will be assessed. b. Embryo quality. This is measured by the Gardner grading system. c. Implantation rate, which is defined by number gestational sacs seen on early pregnancy 6-week ultrasound divided by number of embryos transferred d. Clinical pregnancy rate, which is defined by the number of fetal poles with heartbeat seen on ultrasound divided by the number of embryos transferred e. Live birth rate, which is defined by the number of living babies delivered divided by the number of transfers To determine the effect of IVC with INVOcell device versus conventional IVF while using oral stimulation or minimal gonadotropins stimulation protocols on: a. Live birth rate, which is defined by the number of live births divided by the number of transfers	summary statistics will be provided. This will include mean, standard deviation, minimum,	

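### Clinical pregnancy rate is defined per embryo although the hypothesis concerns women, live birth rate is worded twice, and neither outcome has a per-woman rate

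*Combined protocol and SAP*

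**What the plan says.** The hypothesis in section 4.1 (Project Summary) opens: "In women with infertility requiring IVF, we will see similar clinical pregnancy rates (CPR"). Implantation rate is the primary aim; clinical pregnancy and live birth are secondary aims (sections 4.1 and 7.3).

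Section 7.25 (Statistical Methods) defines the outcomes:

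- Primary: "Implantation rate, which is defined by number gestational sacs seen on early pregnancy 6-week ultrasound divided by number of embryos transferred".
- Clinical pregnancy: "Clinical pregnancy rate, which is defined by the number of fetal poles with heartbeat seen on ultrasound divided by the number of embryos transferred".
- Live birth, in the list of outcomes: "Live birth rate, which is defined by the number of living babies delivered divided by the number of transfers".
- Live birth again, under a repeated lead-in sentence: "Live birth rate, which is defined by the number of live births divided by the number of transfers".

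None of these divides by women, whether randomised, retrieved or transferred. Section 7.25 expects 1 to 3 embryos per patient and plans summary statistics only.

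The background in section 7.6 mixes units. It cites one study with "a clinical pregnancy rate of 43% per embryo transferred from INVO procedure", and another with "pregnancy rate (54.2% INVO-ICSI versus 58.1% ICSI) and implantation rate (31.7% INVO-ICSI versus 33.6% ICSI"), for which no denominators are given.

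**The concern.** CPR and the primary implantation rate share a denominator and differ only in the numerator, heartbeats against sacs. CPR can exceed the implantation rate only if one sac holds two fetuses or a sac is missed at 6 weeks. Otherwise it equals the implantation rate less the sacs without a heartbeat. Followed exactly, the plan reports a close relative of the primary outcome under the pregnancy label and gives no figure for the share of women who became pregnant.

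The live birth entries raise a separate problem. Living babies per transfer counts twins twice, so it is not a proportion and can exceed 100%. Live births per transfer does not say whether it counts babies or deliveries. If it means babies, the two entries are duplicates; if it means deliveries, they conflict.

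The denominators also matter for the comparison of arms. Women are randomised on the day of trigger (section 7.13), before retrieval, fertilisation and transfer. Section 12.2 says that failure of embryo development may be slightly more likely with the device. A randomised woman who reaches no transfer leaves every per-embryo and per-transfer denominator, possibly more often in one arm, so the written rates would not show that loss.

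**Working it through.** The plan gives no calculated figure on this point, so there is none to reproduce. The check asks whether the choice of denominator changes the reported result.

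**1. Counts in one arm.** From the plan: 16 women per arm (section 9.1). Section 7.25 and the recruitment plan in section 10.6 say 20, a separate inconsistency that does not affect the argument. Assumed: one transfer of two embryos per woman; 6 women pregnant, 2 of them with twins; all delivered. Heartbeats, and babies, are then 4 + 2 × 2 = 8.

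| Rate | All 16 have a transfer | 2 of 16 have no transfer, same pregnancies |
|---|---|---|
| CPR as written (heartbeats/embryos) | 8/32 = 25.0% | 8/28 = 28.6% |
| Women pregnant per transfer | 6/16 = 37.5% | 6/14 = 42.9% |
| Women pregnant per woman randomised | 6/16 = 37.5% | 6/16 = 37.5% |
| Live birth, babies per transfer | 8/16 = 50.0% | 8/14 = 57.1% |
| Live birth, deliveries per transfer | 6/16 = 37.5% | 6/14 = 42.9% |
| Women with a live birth per woman randomised | 6/16 = 37.5% | 6/16 = 37.5% |

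When two women reach no transfer and pregnancies are unchanged, the written CPR and both live birth readings go up. Only the rates per woman randomised stay put.

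**2. Number of embryos transferred.** Assumed: heartbeat probability p per embryo from 0.20 to 0.40, and within-woman correlation ρ from 0 to 0.4, in a beta-binomial model. With k embryos, the share of women with at least one heartbeat is

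1 − ∏ over j = 0 to k−1 of [(1−p)(1−ρ) + jρ] / [(1−ρ) + jρ].

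Expected heartbeats per embryo equal p for every k and ρ.

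| p | ρ | Written CPR | Women pregnant, k = 1 | k = 2 | k = 3 |
|---|---|---|---|---|---|
| 0.20 | 0 | 20% | 20.0% | 36.0% | 48.8% |
| 0.20 | 0.4 | 20% | 20.0% | 29.6% | 35.6% |
| 0.30 | 0.2 | 30% | 30.0% | 46.8% | 57.4% |
| 0.40 | 0 | 40% | 40.0% | 64.0% | 78.4% |
| 0.40 | 0.4 | 40% | 40.0% | 54.4% | 62.2% |

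The written CPR stays at 20–40% whatever number is transferred. The share of women pregnant is 30–64% with two embryos and 36–78% with three, so the per-embryo figure cannot stand in for it.

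**3. The plan's own background (section 7.6).** In the cited ICSI comparison, pregnancy rate exceeds implantation rate by 54.2 − 31.7 = 22.5 points and 58.1 − 33.6 = 24.5 points. A CPR written over embryos transferred could hardly exceed the implantation rate at all. In the cited randomised trial, births per blastocyst favour intravaginal culture by 48.5 − 41.7 = 6.8 points, while live birth rate favours IVF by 60 − 55 = 5 points. The denominators of the 54.2/58.1% and 55/60% figures are not stated, so these comparisons only illustrate the point; they do not measure the error in this plan.

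**4. Can the number transferred be read from the plan?** Section 7.9 says "All embryos will be transferred on day 3", section 7.25 expects 1 to 3 embryos, and section 7.14 allows embryos to be frozen for later use. The attached IVC protocol is not among the text available. One transfer per woman is therefore not assured, nor is one embryo per transfer, and these passages need to be reconciled.

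**The case against.** The written definition is explicit and has a precedent in the plan: the 43% in section 7.6 is per embryo transferred. The reference to women in the hypothesis names the population and need not fix a denominator. Live birth is already per transfer. If each woman has one transfer and live births means deliveries, that entry is a rate per woman transferred. Heartbeat and sac are different events, and the plan gives no loss rate between them, so how closely CPR tracks implantation is not quantified. Randomising at trigger keeps earlier cancellations out of both arms, and the size of any unequal loss afterwards is unknown. All the event counts above are assumed. These are secondary outcomes of a descriptive pilot with no test or margin, and at 16 or 20 per arm the 95% half-width for a difference in per-woman rates near 55% is about 35 or 31 points.

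Much of this is fair and limits the size of the claim. The precedent is a reason to keep the per-embryo rate, under its own name. It does not supply the share of women pregnant. The favourable reading of live birth still needs a decision between babies and deliveries, and it still omits randomised women without a transfer. Pilot status does not remove the point: when the analysis is descriptive, the definitions settle what is reported and what a larger trial would inherit.

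**Conclusion.** The concern holds and should be fixed. As written, CPR is a heartbeat-based implantation rate, live birth rate has two wordings and no rule for multiples, and no pregnancy or live birth rate is defined over women. In the assumed arm of 16, CPR is 25% where 37.5% of women are pregnant, and live birth rate is 50% or 37.5% depending on the reading.

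These sizes rest on the assumed counts. The babies-against-deliveries gap vanishes if there are no multiples. The CPR gap per transfer vanishes if, in addition, every transfer is of one embryo. The gap between per-transfer and per-randomised rates vanishes only if every randomised woman has exactly one transfer. The primary implantation definition is not affected, and better definitions will not make a pilot of this size able to show similarity.

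**What to change.** In section 7.25:

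- Define CPR as the number of women with at least one fetal pole with heartbeat, divided by women randomised.
- Define live birth rate once, as the number of women with at least one live-born baby, divided by women randomised, and delete the duplicate entry.
- Count women with no transfer as not pregnant in both rates. State that the rates refer to the randomised cycle, and say how women whose embryos are all frozen and women lost to follow-up are counted.
- Give per-transfer rates as supporting results.
- Keep heartbeats per embryo transferred under its own name, so that it can still be set beside the cited 43%.
- Report multiple pregnancies and babies born separately.

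The cost is a rewording of two definitions plus the short counting rules. The same ultrasound and delivery data are used, and neither the sample size nor the primary outcome changes.
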